## 9 ETHICAL CONSIDERATIONS

### 9.1 General considerations

This study must be carried out in accordance with the provisions of this protocol and the standards of Good Clinical Practice (GCP), as described in:

- ICH Harmonised Tripartite Guideline for Good Clinical Practice, 1996. Directive 91/507/EEC: Good Clinical Practice Guidelines for trials on medicinal products in the European Community.
- **Helsinki Declaration** in its latest revised version (Fortaleza, 2013) (Annex-1).

The study will only begin after obtaining written authorisation from the Ethical Review Committee of the Macarena-Virgen del Rocío University Hospitals in Seville, which act as a reference centre (rERC).

Except for emergency situations, changes or deviations from the protocol will not be permitted without documented approval.

The rERC shall be informed of any changes and shall approve in writing any changes or deviations that may increase the risks of the subject and/or may adversely affect the rights of the patient or the validity of the research. This stipulation does not apply to changes made to reduce inconveniences or prevent risks to subjects or to changes affecting the administrative aspects of the study (e.g. change of monitor).

## **9.2 Assessment of the risk-benefit for the research patients**

In any case, the patient will receive a specific therapeutic alternative, in accordance with the diagnosis established by the investigator, so the suitability of the study treatments will not result in an increase in risk for the patient.

If the investigator or patient perceive a lack of effectiveness of the treatment, the patient may be rescued with the therapeutic alternative considered within the study.

## **9.3 Information sheet and informed consent (Annexes 1 and 2)**

The investigator is responsible for ensuring that the patient (and/or legally authorised representative) understands the risks and benefits of her participation in the study, answering any questions that may be raised during the study, and sharing any new information that could influence her decision to continue to participate in the study in a timely manner.

The patient (or her legal representative) shall be informed of the characteristics of the CT, orally and in writing, by means of the PATIENT INFORMATION SHEET.

Finally, after being fully informed of the implications and restrictions of the protocol, having answered her questions and before starting the study, the patient will be asked to provide written INFORMED CONSENT. The patient information sheet model and the informed consent form are attached as an annex to this protocol. By signing and dating the informed consent form, the subject declares her voluntary participation and intention to comply with the Study Protocol and the Investigator Instructions and to respond to the questions raised during the Study.

The subject will keep the information sheet throughout the study, with all relevant study information, including the investigator's contact information. The investigator must keep the informed consent in the study file.

#### **9.4 Review of the Ethics Committee**

This protocol will be approved by the Ethical Review Committee of the Virgen Macarena-Virgen del Rocío University Hospitals in Seville, which will act as a reference committee for the other participating centres.

Any member of the Ethics Committee who has direct contact with this study as an investigator or as a member of staff of the centre will abstain from voting to approve the protocol.

All changes to the protocol will be specified as an amendment. The method for performing amendments will follow the standardised procedures according to RD223/2004.

#### **9.5 Data confidentiality**

By signing the protocol, the investigator agrees to keep all the information provided by the Sponsor in strict confidence and to insist on his team and the rERC keeping this confidence. The study documents provided by the Sponsor (protocols, investigator manual, CRFs and other materials) must be conveniently stored in the investigator's file, to ensure their confidentiality. The investigator will in turn ensure that the investigator's file is kept in accordance with the conditions specified in Directive 2001/20/EC.

The investigator will ensure the anonymity of the participants. Both in CRFs and other CT documents, subjects cannot be identified by their names but by an identification code. The investigator will keep a record of the inclusion of subjects showing the codes, names and contact information.

The information provided to the investigator by the Sponsor may not be disclosed to third parties without the direct written authorisation of the sponsor, except to the extent necessary to obtain the informed consent of the patients who wish to participate in this CT.

The information obtained will be considered strictly confidential on the basis of Organic Law 15/1999, of 13 December, on Personal Data Protection. (Official State Gazette No. 298, of 14-12-1999, p. 43088-43099) and its development

regulations. Medical data will be collected in accordance with Recommendation No. R (97) 5, of 13 February 1997, by the Committee of Ministers of the Council of Europe to the Member States on Medical Data Protection.

## **9.6 CRF records and reports**

The investigator must ensure the accuracy, completion and relevance of the data communicated to the sponsor in the CRF and in all the reports requested. The data will be recorded in an online CRF to which only the investigator will have access through a user and password, both of which will be personal and non-transferable. All data obtained will be stored in an electronic file restricted to the staff of each centre and for which the principal investigator will be responsible.

Any change or correction to a CRF must be requested to the CRO responsible for monitoring, Clever Instruments S.L., by contacting the person responsible for the *data management* designated by the study sponsor. Changes must be documented and the investigator must keep records of changes and corrections.

The investigators or the institution must keep the CT documents, as required by applicable regulations. The investigator or institution must take measures to prevent the accidental or premature destruction of these documents.

At the request of the monitor, auditor, ERC or regulatory authority, the investigator/institution must have all records related to the CT available.

### **9.6.1 Monitoring Reports**

The sponsor or CRO must send written summaries of the trial status to the rERC annually, or more frequently, if required by the rERC.

The sponsor or CRO must provide timely written reports to the rERC and, where relevant, to the institution on changes that significantly affect the development of the trial and/or increase the risk to the subjects. The investigator must supervise and sign these reports.

### **9.6.2 Safety Reports**

The sponsor must be immediately informed of all serious adverse events, except those specified in the protocol or other document. These will be promptly reported in writing in detail and within the periods specified by the sponsor in the protocol. These follow-up reports must identify the subjects using the codes assigned in the CT and not by name, personal identification numbers and/or addresses.

### **9.6.3 Protocol Premature Termination or Suspension**

If the study ends prematurely or is suspended for any reason, the investigator/institution must promptly inform the subjects of the study, providing them with appropriate therapy and follow-up. In addition:

- If the investigator terminates or suspends the study without prior agreement with the sponsor, the investigator must inform the institution where relevant, and the investigator/institution must promptly inform the sponsor and the ERC, as well as send a detailed written explanation of the termination or suspension to the sponsor and the ERC.
- If the sponsor terminates or suspends the study, the investigator must promptly inform the institution where relevant and the investigator/institution must promptly inform the ERC, sending a detailed written explanation of the termination or suspension.
- If the ERC withdraws the approval of the study, the investigator must inform the institution where relevant and the investigator/institution must promptly notify the sponsor and provide a detailed written explanation.

### **9.6.4 Final Investigator Report**

When the study is completed, the investigator, where relevant, must inform the institution. The investigator/institution must provide the ERC with a summary of the study's results.

## **9.7 Monitoring**

It is established that the study will be carried out at regular intervals. Monitoring will be carried out by the monitor(s) designated by the Sponsor. Regular contacts will be established between the Monitor(s) and the Investigator.

The Monitor will be responsible for verifying compliance with the protocol and the integrity, consistency and reliability of the data entered in the CRFs. To do this, the monitor must be able to access the participant's medical history and other documents. The investigator or his collaborators agree to cooperate with the monitor to ensure that the detection of any problem during the monitoring is resolved.

Extraordinary audits can be carried out to guarantee the validity of the study data and compliance with the regulations in force.

## **9.8 Study budget**

The economic aspects of the study are detailed in the corresponding annex in a separate document.

## **9.9 Insurance**

The sponsor of the study (Laboratorios Ordesa S.L.) will subscribe to an insurance policy that covers any damages that may be caused to the participants as a result of the study.

This insurance will also cover the responsibilities of the sponsor, the investigator and his collaborators and the head of the centre where the clinical study is carried out.

# **10 PRODUCT PREPARATION AND CONSERVATION**

## **10.1 Conditioning**

The product under study (vaginal capsule with 150 mg of boric acid, *Lactobacillus gasseri*, *Lactobacillus rhamnosus*.) must be received by the hospital pharmacy, which will be responsible for the control, distribution and

return of the product under research. Enough product for 70 patients will be assigned, taking into account that the study group must receive product for one treatment week (1 box) during the baseline visit.

### **10.2 CT sample, product or treatment labelling**

As this is an open study, products administered to patients will not have any special labelling and will be labelled in the same way as they are usually on the market.

### **10.3 Conservation, distribution and return**

Products provided for the CT must be stored at room temperature in a restricted area free from extreme environmental conditions. This should be an area that can be closed, with access limited to the investigator.

When received, an inventory of the shipment must be made. The document must be signed by the investigator or authorised person and a copy will be sent to the Monitor and another to the Investigator's Archive.

The investigator will be responsible for the return of the products, and will document any discrepancies in the formula stock records.

## **11 ADVERSE EVENTS**

The Adverse Events (AE) that appear during the study will be assessed. An AE is any harmful event in a patient after randomisation and during a study, even if it is considered not related to the treatment of the study. ***In this CT, AEs will be collected and recorded in the CRF, provided that they are serious (if they cause clinical signs or symptoms and are considered clinically significant) and/or are related to the treatments under study.***

Diseases or medical conditions that were present before starting the medication under study will only be considered AEs if there is a worsening after the start of the study treatment (any procedure specified in the protocol).

As far as possible, AEs will be described according to:

- Duration (start and end dates).
- Degree of severity (mild, moderate, severe).
- Relationship with medication under study (suspected/not suspected).

- Action(s) taken to correct it.

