#### **3.2 Secondary objectives**

- To determine the incidence of recurrence/relapse at 3 months.
- To assess the level of post-treatment vaginal flora restoration.
- To characterise the different symptomatic and microbiological profiles of VV.
- To assess the tolerance and safety of the product.

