### 7.3 End points

- Number of patients with VV recurrence during the follow-up period in each treatment group (incidence of recurrences after 3 months).
- Number of patients with resolved symptoms in each group 2 weeks after finishing the treatment.
- Changes in vaginal pH level in each group.
- Number of patients with “*clue cells*” or hyphas in the fresh smear.

- Profile and proportion of pathogen isolation in culture.
- Increase in the population of *Lactobacillus spp.* post-treatment.
- Rescue success rate in different scenarios.
- Relationship between compliance and treatment effectiveness.
- Relationship between compliance and recurrence after 3 months.
- Percentage of cases with good treatment tolerability.
- Rate of adverse events.
- Treatment tolerability.
- Proportion of patients with mixed infections (VC + BV).

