### **8.2 Objectives of the study**

The analysis of the main objective will focus on the comparison of the effectiveness of the product under study (boric acid + *L. gasseri* and *L. rhamnosus*) and that of the control treatment with solid vaginal forms, according to the usual clinical practice (clotrimazole or clindamycin) and assessed according to the patient's clinical symptom scores (VAS, Sobel score) approximately 2 weeks after the end of the treatment. To do this, T tests for independent samples or non-parametric Mann–Whitney U tests will be used.

For the secondary objectives, the level of restoration of vaginal flora will be assessed by comparing the *Lactobacillus* count in baseline discharges and 2 weeks after treatment through T tests for related samples or non-parametric

Wilcoxon or McNemar tests. The incidence of recurrences/relapses at 3 months will be studied by means of proportion comparison tests (Pearson's chi-squared test). The characterisation of the different symptomatic and microbiological profiles of VV, as well as the tolerability, compliance and adverse events, will be analysed through descriptive statistics.

The possibility of carrying out additional analyses, depending on the results, with the relevant statistical tests in each case is not ruled out.

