### **11.1 Types**

Any adverse and unintentional sign (abnormal and clinically significant analytical result) associated or not to the use of the drugs will be considered an adverse event.

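### The reported adverse event rate will be that of a filtered subset, because section 11 keeps some of the AEs it defines out of the CRF

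*Combined protocol and SAP*

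**What the plan says.** Section 11 counts harmful events after randomisation as AEs "even if it is considered not related to the treatment of the study". Section 11.1 takes the same line and brings in laboratory findings: "abnormal and clinically significant analytical result) associated or not to the use of the drugs will be considered an adverse event".

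The next sentence of section 11 narrows what is kept: "AEs will be collected and recorded in the CRF, provided that they are serious". The explanation of that word, and the alternative way in, follow at once: "if they cause clinical signs or symptoms and are considered clinically significant) and/or are related to the treatments under study".

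Section 3.2 sets the safety objective, "To assess the tolerance and safety of the product". Section 7.3 lists "Rate of adverse events" without qualification, beside two tolerability items, one of them "Percentage of cases with good treatment tolerability". Section 8.1 describes the variables held in the CRF. Section 8.2 adds that the VV profiles, "as well as the tolerability, compliance and adverse events, will be analysed through descriptive statistics".

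Section 11.3 uses *serious* in a different sense, based on outcome: death, threat to life, hospitalisation, lasting disability or congenital anomaly. Sections 6.1 and 10.2 confirm that the trial is open.

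**The concern.** The definition and the end point are unrestricted, but the data that feed the end point are restricted. A reader of the results who sees an AE rate will take it to cover AEs as the protocol defines them. It will cover only those that the investigator, knowing the treatment, judged to be related or to be both symptomatic and clinically significant.

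The choice of word makes this worse. *Serious* has one meaning in the filter sentence and another in section 11.3. An investigator who carried the section 11.3 meaning back to the filter would record far fewer events, and practice could then differ between centres.

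What is at stake is the interpretation of one descriptive safety end point under a secondary objective. If an event is not entered, the plan names no other source from which the analysis could recover it.

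**Working it through.** The plan states no AE rate, so there is no figure to reproduce. The check compares the definition with the filter and then asks how far the result could move.

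**Step 1. Which AEs reach the CRF, using the meaning of *serious* given in section 11?**

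| Related to a study treatment? | Causes signs or symptoms? | Judged clinically significant? | Recorded? |
|---|---|---|---|
| Yes | either | either | Yes |
| No | Yes | Yes | Yes |
| No | Yes | No | No |
| No | No | Yes | No |
| No | No | No | No |

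The third row is an AE under section 11 if the event is harmful. The fourth includes significant analytical results, which section 11.1 expressly counts. That group is probably small, because the samples described in section 6.3.3 are of vaginal discharge only. The fifth row would seldom meet the definition at all.

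**Step 2. Is there another recording route?** Section 11.3 collects serious events with suspected causality only. The home CRF in section 6.3.3 is a follow-up diary and is not named as a source of AEs. No other section provides a route.

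**Step 3. Direction.** Let *f* be the share of defined AEs that fall in the unrecorded rows. Then, counting events:

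recorded rate = true rate × (1 − *f*)

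The recorded rate cannot exceed the true rate. The documents do not give *f* or a true rate. As an illustration only, assume a true rate of 0.30 events per patient:

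- *f* = 0.10: 0.30 × 0.90 = 0.27
- *f* = 0.25: 0.30 × 0.75 = 0.225
- *f* = 0.50: 0.30 × 0.50 = 0.15

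If *f* = 0, nothing is lost.

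**Step 4. Weight of one event.** Section 6.8 gives a minimum of 50 patients and section 6.5 a 1:1 ratio, so 50 / 2 = 25 per arm. Section 7.3 does not say whether the rate counts patients or events.

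- If patients: one patient whose only AE is left out lowers the arm's rate by 1 / 25 = 4.0 percentage points.
- If events: one lost event lowers it by 1 / 25 = 0.04 events per patient.

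This is the weight of one patient or event in a trial of this size. It does not estimate how many are lost.

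**The case against.** The best defence is that this is an openly stated scope rule. The filter directly follows the definition and is worded as specific to this trial. The trial is a postmarketing pilot, AEs are only described, and selective collection can be a legitimate choice. The events dropped are those of least interest. The Sobel score, the examinations at the control visits and the tolerability end points will pick up some local symptoms. Section 11 also asks for a mild grade and a not-suspected category, so some mild and some unrelated events are clearly expected in the CRF.

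Much of this stands: the loss is limited, and a filter would be acceptable if the end point declared it. But section 7.3 does not declare it, and results are read apart from section 11. That some mild or unrelated events pass the filter does not mean that all do. The CRF forms are not among the documents, so what else they capture is unknown.

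Four stronger readings are tempting but not supported:

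- **Only related events and section 11.3 serious events are kept.** The explanation inside the filter sentence is broader and governs it. The narrower reading is a risk of misapplication.
- **The AE comparison is biased between arms.** Section 11.2 lists signs for the study product only, and relatedness is judged with treatment known, so differential recording is possible. Nothing shows it, and section 8.2 plans no between-arm test of AEs.
- **Two of the five causality terms in section 11.3 have no clear side.** The definition of *unlikely related* reads as not related. Only *not assessable* is open.
- **The weight of one patient can also be worked out at 35 per arm.** The figure of 70 in section 10.1 concerns supply of the study product and does not support that split.

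Whether section 11.3 limits the immediate notification of serious events to the sponsor in section 9.6.2 is a separate matter with no bearing on this rate.

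**Conclusion.** The mismatch is real and minor. Followed as written, the plan yields the rate of AEs that are related, or symptomatic and clinically significant, under a label that promises the rate of all AEs. The reported rate can only be equal to or below the rate under the protocol's own definition.

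The size of the shortfall cannot be computed, is probably small and may be zero. This conclusion assumes that investigators apply *serious* as section 11 explains it; if they apply section 11.3 instead, the shortfall is larger. Efficacy is unaffected. High confidence attaches to the textual conflict and not to its numerical effect.

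**What to change.** - In section 11, replace the filter sentence with a statement that all AEs after randomisation are recorded in the CRF, whatever their seriousness or relationship to treatment.
- Use *serious* only for the section 11.3 criteria.
- Replace the two-level descriptor in section 11 and the five-term scale in section 11.3 with one causality scale for all three products. State which terms count as related, including where *not assessable* goes.
- In sections 7.3 and 8.2, define the end point as the number and percentage of patients with any AE, any related AE and any serious AE, reported descriptively by treatment received at onset. Show events after a crossover under section 6.2.3 separately, since a patient may receive more than one product.
- If the filter is kept, rename the end point to match it and state the filter beside the result.

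The cost is protocol wording and slightly more CRF entry for about 50 patients followed for 3 months. Background events will raise the all-AE rate, so the related-AE rate should stand beside it. Renaming alone costs almost nothing but leaves the events unrecorded.

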### *6.2.3 Rescue criteria*

In cases where the patient requires "rescue treatment", the treatments will be crossed. In the event of changing treatment group (crossover), the patient will be considered to be back at V0 and the tests/examinations corresponding to the baseline visit will be repeated.

The patient will change group to receive alternative treatment in the following cases:

- Patient with hypersensitivity to the first assigned treatment.
- Worsening of symptoms within 3-4 days of starting the assigned treatment.
- Evidence or indications of lack of effectiveness after the first assigned treatment.
- Patient who demonstrates a willingness to change treatment.
- In cases where the perceived lack of effectiveness is associated with a suspected mixed aetiology infection (candidal and bacterial):
  - If they are in the control group, they will be changed to the treatment under study (boric acid + *L. gasseri* and *L. rhamnosus*).
  - If they are in the study group, they will be changed to the antifungal treatment (Gine-Canesten®; Clotrimazole 100 mg). If this treatment fails, BV will be treated with antibiotic treatment (Dalacin®; Clindamycin 100 mg).

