## 7 VARIABLES AND MEASURING INSTRUMENTS

### 7.1 Main assessment variables

- Presence and severity of clinical signs/symptoms associated to VV that the patient presents.
- Sobel score: Semi-quantitative scale where itching, erythema, oedema and stinging are indicated from 0 to 3: Absent (0), mild (1), moderate (2), severe (3).
- Vaginal pH (to be determined by placing a vaginal discharge sample in contact with reactive pH indicator strips).
- Fresh vaginal smear (presence of “*clue cells*” or hyphas).
- Vaginal discharge sample culture.
- *Lactobacillus spp.* count in vaginal discharge.
- Relevant gynaecological history (including previous VV episodes).
- Compliance with the treatment and the gynaecologist’s recommendations.
- Adverse Events.

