### **11.2 Clinical signs secondary to the use of the study drug**

- i. Vaginal itching sensation
- ii. Water discharge during treatment
- iii. Vaginal erythema
- iv. “Sandy” sensation during sexual intercourse
- v. Acute systemic toxicity due to boric acid
- vi. Chronic toxicity due to the use of boric acid
- vii. Bacteraemia caused by *Lactobacillus spp.*

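### Worsening of the vulvovaginitis under study can enter the adverse event rate, and early product irritation can be read as worsening; the plan should tabulate the overlap separately

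*Combined protocol and SAP*

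**What the plan says.** All references are to the combined protocol and SAP.

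- **AE definition (section 11).** "An AE is any harmful event in a patient after randomisation and during a study", whether or not it is related to treatment. Conditions that the patient already had at entry are covered by a separate rule: they "will only be considered AEs if there is a worsening after the start of the study treatment". The disease under study is not excepted.
- **Recording filter (section 11).** Not every AE is entered on the case report form. The condition for entry reads: "provided that they are serious (if they cause clinical signs or symptoms and are considered clinically significant) and/or are related to the treatments under study".
- **End point (section 7.3).** "Rate of adverse events", with no further rule for the numerator. Section 8.2 analyses AEs descriptively.
- **Rescue (section 6.2.3).** One trigger for changing treatment is "Worsening of symptoms within 3-4 days of starting the assigned treatment". At the one-week call (section 6.3.4), deterioration and lack of effectiveness share a row that leads to rescue.
- **Listed effects of the study product (section 11.2).** These include itching, erythema and "Water discharge during treatment".
- **Effectiveness measures.** Section 6.3.3 records itching, erythema and abnormal discharge among the VV signs. The Sobel score in section 7.1 is a "Semi-quantitative scale where itching, erythema, oedema and stinging are indicated from 0 to 3". Section 8.2 compares the VAS and Sobel scores about two weeks after treatment ends.

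**The concern.** Tolerance and safety is a secondary objective (section 3.2), separate from effectiveness. The definitions let one event bear on both.

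In one direction, every patient has VV at baseline, so a patient whose VV gets worse has a pre-existing condition that worsened. If the recording filter admits the event, it counts as an AE. The less effective arm could then show the higher AE rate with no difference in harm.

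In the other direction, irritation caused by the product looks like the disease. If it is read as worsening, the patient changes treatment and returns to V0. The rescue data then carry a tolerability effect under the name of worsening.

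The misreading may also differ by arm. The trial is open, and the section 11.2 list covers the study product only, so the same itch has a listed product cause in one arm and none in the other.

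**Working it through.** The plan states no AE, worsening or irritation rate, so there is no figure of its own to reproduce. The check compares the text and then illustrates size on assumed rates.

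**1. Can VV worsening reach the AE rate?** It meets the pre-existing-condition rule. It then has to pass the filter. Section 11 glosses serious as causing signs or symptoms and being clinically significant. That is far wider than the section 11.3 list (death, threat to life, hospitalisation and so on), and worsening that prompts a change of treatment can meet it. VV that persists without getting worse does not meet the rule. So the route is open, but it is not automatic.

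**2. How far do product effects and VV signs overlap?** Itching and erythema are 2 of the 4 Sobel items, or 2 × 3 = 6 of 4 × 3 = 12 points. Discharge is a recorded VV sign but not a Sobel item.

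**3. Size, worsening counted as AE.** Let r be the true risk of other AEs, equal in both arms; w the risk of VV worsening; and f the share of worsening that is recorded. Assuming independence:

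AE rate = 1 − (1 − r)(1 − f·w); gap between arms = (1 − r)·f·(difference in w).

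With r = 5% (assumed):

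| Worsening (assumed) | f = 1 | Gap | f = 0.5 | Gap |
|---|---|---|---|---|
| 5% v 10% | 1 − 0.95×0.95 = 9.75% v 1 − 0.95×0.90 = 14.5% | 4.75 points | 7.4% v 9.75% | 2.4 points |
| 10% v 20% | 14.5% v 24.0% | 9.5 points | 9.75% v 14.5% | 4.75 points |
| 15% v 30% | 1 − 0.95×0.85 = 19.25% v 1 − 0.95×0.70 = 33.5% | 14.25 points | 12.1% v 19.25% | 7.1 points |

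With f = 0 the rates are 5% v 5%. Raising r to 20% with 10% v 20% worsening gives 28% v 36%, a gap of 8 points.

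Sections 6.1 and 6.8 plan at least 50 patients at 1:1, about 25 per arm, so one patient is 4 points. The first row at f = 1 is 25 × 0.0475 ≈ 1.2 patients and the last is 25 × 0.1425 ≈ 3.6.

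**4. Size, irritation read as worsening.** Let w be true worsening, i the irritation risk in the product arm, and g the share of irritation read as worsening. The rise in worsening-triggered rescue is (1 − w)·g·i. With w of 10% to 20% and i of 5% to 20% (assumed) and g = 1, the rise runs from 0.80 × 0.05 = 4 points to 0.90 × 0.20 = 18 points, or 1 to 4.5 of 25 patients. With g = 0.5 it is 2 to 9 points.

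**The case against.** The strongest reply is that the plan already holds part of the separation.

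- Section 11 asks for start and end dates, relationship and action taken.
- The causality scale in section 11.3 has a category for events due to the patient's clinical condition.
- Section 6.2.3 lists hypersensitivity, worsening and lack of effectiveness as distinct reasons, and section 6.3.3 distinguishes an ineffective treatment from an intolerable one.
- Section 7.3 lists tolerability apart from the AE rate.
- The CRF is not in the documents and may already capture the reason for a change.
- AEs are only described, in a pilot, so no planned safety test can be misled.

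Much of this stands, and it rules out the reading that nothing in the plan keeps the two apart. It does not close the gap. Relationship is not used to define the AE rate. On the causality scale, an event counts as related only if the clinical condition cannot explain it, while the potentially related category allows that it may; itching in a VV patient will often fall in the latter. The one-week call has no row for intolerance.

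Three further inferences are tempting and are not supported:

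- **That rescue is scored as treatment failure.** No section says so. The patient returns to V0, rescue success is its own end point, and a patient may change simply because she wishes to.
- **That the main comparison is contaminated to the same degree.** It is made about two weeks after treatment ends, when irritation confined to the course may have gone, and discharge is not a Sobel item.
- **That all treatment failure counts as harm.** Only worsening meets the rule, and only if it passes the filter.

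**Conclusion.** The point holds in limited form. As written, section 11 lets worsening of the study VV into the AE rate when it is symptomatic and judged clinically significant, and section 7.3 does not take it out. In the other direction, early irritation can be read as worsening at the 3-4 day or one-week rescue decision; the two-week score comparison is less exposed.

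The size cannot be fixed from the documents. With full recording, a 5% true AE risk and independence, the spurious AE gap is about 5 points for 5% v 10% worsening and about 14 points for 15% v 30%. For those assumed rates these are upper bounds: half recording halves them, and the gap vanishes if worsening is equal in both arms or is not recorded. The 14-point figure should not be taken as a forecast, since it needs 30% of one arm to get worse, not merely fail to respond, and every case to be recorded.

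This is a clarification of a descriptive end point. It is worth making before data are collected, because onset and reason for change may not be recoverable later.

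**What to change.** 1. **Sections 11 and 7.3.** State that worsening of the VV under study is tabulated apart from other AEs, and show the AE rate with and without it. Events meeting the serious criteria of section 11.3 are still reported as such.
2. **Overlapping local symptoms.** Put new or increased itching, erythema or discharge in a single separate category, without forcing attribution to product or disease. Record it identically in both arms over one fixed window from the start of treatment. The window should not be the treatment course, because courses last 7, 6 and 3 days (section 1.16) and unequal windows would by themselves tilt the count against the study product. An early flare that fits both this category and item 1 is counted once, here. Show the AE rate with and without this category too.
3. **CRF.** Record the reason for each treatment change (intolerance, worsening or lack of effect, patient wish), if this is not already done.

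The cost is a few lines of wording, at most one CRF field and slightly more tabulation. Attribution stays imperfect, which is why both versions of the rate are shown. No rescue or treatment rule changes.
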